16.8.2. Additional Efficacy and Pharmacodynamic Analyses

All efficacy and PD endpoints described in Section 16.3.2 and Section 16.3.3 will be summarized. Efficacy endpoints that are defined as continuous variables will be analyzed using a similar model as described for the primary efficacy endpoint if they are collected at multiple post-baseline visits; otherwise, they will be analyzed using analysis of covariance (ANCOVA) adjusted for randomization strata and baseline measurements of the response parameter of interest. For continuous endpoints that do not meet the normal distribution assumption, they will be analyzed by stratified Hodgens-Lehmann estimates for the median, with the 90% confidence intervals derived using stratified Van-Elteren test. Other endpoints defined as response proportions will be analyzed using a Cochran-Mantel-Haenszel test stratified by randomization strata. Time-to-event data will be analyzed using a Cox regression model, stratified by randomization strata.

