### 2.2 Secondary Study Objectives

The secondary objectives of this study are:

- To evaluate the safety and tolerability of EP262 compared to placebo in subjects with CSU
- To evaluate the efficacy of EP262 compared to placebo in subjects with CSU as assessed by the following:
  - Pruritus severity
  - Hive severity

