#### 3.4.1.2 Secondary Efficacy Variables

All efficacy assessments will be performed as indicated in the Schedule of Assessments (Appendix A) of the clinical study protocol. Secondary efficacy endpoints include the following:

- Change from baseline to Visit 4 (Week 6) in the sum of the daily ISS over a 7-day period (ISS7)
- Change from baseline to Visit 4 (Week 6) in the sum of the daily HSS over a 7-day period (HSS7)

Description of the UAS is provided in [Section 3.4.1.1](#). The ISS7 is the sum of the daily ISS over a seven-day period; similarly, the HSS7 is the sum of the daily HSS scores over a seven-day period. The ISS7 and HSS7 scores range from 0 to 21, where 0 is no itching/no wheals and 21 is the worst possible score. The MID for ISS7 and HSS7 is considered a reduction in baseline of  $\geq 5$  for each ([Mathias 2012](#)).

[figure not shown]
The same general windowing rules used to determine analysis visits for the UAS7 described in [Section 3.4.1.1](#) will be applied to the ISS7 and HSS7 endpoints. The ISS7 can be derived if the minimum required number of ISS scores are reported within each

[figure not shown]
analysis visit. Similarly, the HSS7 can be derived in the minimum required number of HSS scores are reported within each analysis visit.

[figure not shown]
*3.4.1.3 Exploratory Efficacy Variables*

[figure not shown]
[REDACTED]

[REDACTED]

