#### **4.1.1 Reporting Conventions**

Tables will be summarized by treatment group within each study part, as well as by pooled placebo across both study parts (if applicable). All tables, exclusive of efficacy, PD and PK analyses, will also include a column for all subjects combined as well as a treatment column for all EP262 doses pooled together across Part 1 and Part 2 (if available). In general, all data collected and any derived data will be presented in subject data listings, for all enrolled subjects. Listings will be ordered by study part, site, subject number, treatment group, and assessment or event date. The treatment group presented in listings will be based on the planned assignment, unless otherwise noted.

In general, continuous variables will be summarized to indicate the study population sample size (N), number of subjects with available data (n), mean, standard deviation (SD), standard error (SE), median, first (Q1) and third (Q3) quartiles, minimum, and maximum values. Categorical variables will be summarized by the population size (N), number of subjects with available data (n), number of subjects in each category, and the percentage of subjects in each category. Unless otherwise noted, the denominator to determine the percentage of subjects in each category will be based on the number of subjects with available data. Select ordinal data may be summarized using both descriptive statistics and counts and percentages of subjects in each category, as appropriate.

Non-zero percentages will be rounded to one decimal place. Rounding conventions for presentation of summary statistics will be based on the precision of the variable of summarization, as it is collected in its rawest form (i.e., on the eCRF or as provided within an external file) and are outlined as follows:

- The mean and median will be rounded to one more decimal place than the precision of the variable of summarization;
- Measures of variability (e.g., SD, SE) will be rounded to two more decimal places than the precision of the variable of summarization; and
- Minimum and maximum values will be presented using the same precision as the variable of summarization.

Other statistics (e.g., confidence intervals [CIs]) will be presented using the same general rules outlined above, or assessed for the most appropriate presentation based on the underlying data.

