#### ***4.4.4 Secondary Endpoint Analysis Methods***

The secondary endpoints of change from baseline to Visit 4 (Week 6) in ISS7 and HSS7 will be summarized with descriptive statistics. Descriptive statistics will be presented for observed values and changes from baseline at each analysis visit where parameters are to be derived.

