##### ***4.4.6.2 Handling of Dropouts or Missing Data***

For assessment of responder endpoints, subjects with missing data at the time point of interest will not be analyzed; only observed values will be used.

Derivations of the weekly UAS7, ISS7, [REDACTED] scores will consider the minimum daily score requirement and management of missing scores as defined in [Section 3.4.1.1](#).

The [REDACTED] data collection does not allow for individual questions to be skipped within a questionnaire response; therefore, the management of missing scores relative to the derivation of each total score and the dimension scores is not required.

For the primary endpoint, treatment groups will be compared for observed and change from baseline in weekly UAS7 score using a MMRM. The model will include fixed treatment group by week interaction, the stratification factor of prior omalizumab use (randomization strata), and the UAS7 baseline value as a covariate. The Kenward and Roger method will be used to calculate the denominator degrees of freedom for the test of fixed effects. All other endpoints are summarized descriptively and are based on observed data.

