#### **4.4.6.3     *Interim Analyses and Final Analysis***

The sponsor will perform an interim analysis after all subjects have completed Part 1. Part 1 subject data will be locked and Part 1 treatment assignments will be unblinded to the study team to allow for statistical analysis of the primary endpoint, specific to the Part 1 interim analysis and treatment groups. The whole result package (all SAP-defined analysis, specific to Part 1) will be delivered. Hypothesis testing will be based on the active arms in Part 1 versus the part 1 placebo group.

The final analysis will be conducted after all subjects have completed Part 1 and Part 2, if applicable. The two study parts will be pooled, and statistical analysis including hypothesis testing will be performed between each active arm versus the pooled placebo groups from Part 1 and Part 2 (if applicable) for the primary endpoint. The whole result package (all SAP-defined analysis incorporating both Part 1 and Part 2 subjects) will be delivered.

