Efficacy endpoints that are defined as continuous variables will be analyzed using a similar model as described for the primary efficacy endpoint if they are collected at multiple post-baseline visits; otherwise, they will be analyzed using analysis of covariance (ANCOVA) adjusted for randomization strata and baseline measurements of the response parameter of interest. For continuous endpoints that do not meet the normal distribution assumption, they will be analyzed by stratified Hodgens-Lehmann estimates for the median, with the 90% confidence intervals derived using stratified Van-Elteren test. Other endpoints defined as response proportions will be analyzed using a Cochran-Mantel-Haenszel test stratified by randomization strata. Time-to-event data will be analyzed using a Cox regression model, stratified by randomization strata.

No hypothesis testing will be conducted for secondary and exploratory endpoints; only descriptive analysis results will be provided. Given the limited sample size and the nature of Phase 2 as a proof-of-concept (POC) study, hypothesis testing for secondary endpoints may not be considered appropriate and has been excluded from the SAP.

In addition, supplemental evaluation of normality assumptions and use of the stratified Hodgens-Lehmann and stratified Van-Elteren test (as needed) will not be utilized. Given the sample size of the study, the estimates are assumed to be valid based on Central Limit Theorem, even if select data are not normal.

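### The SAP drops the protocol's model for ISS7 and HSS7, so the comparative secondary objective has no planned adjusted difference from placebo and no confidence interval

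*SAP*

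**What the plan says.** SAP 2.2 states the secondary efficacy objective as a comparison: "To evaluate the efficacy of EP262 compared to placebo in subjects with CSU as assessed by the following", followed by pruritus severity and hive severity. The endpoints are change from baseline to Week 6 in ISS7 and HSS7.

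Protocol 16.8.2 sets the method: "Efficacy endpoints that are defined as continuous variables will be analyzed using a similar model as described for the primary efficacy endpoint", provided they are collected at more than one post-baseline visit. Protocol 16.8.1 defines the treatment effect in that model as the EP262-minus-placebo contrast of LS means.

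The SAP replaces this in three places:

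- 4.4.4: "The secondary endpoints of change from baseline to Visit 4 (Week 6) in ISS7 and HSS7 will be summarized with descriptive statistics".
- 4.4.6.2: "All other endpoints are summarized descriptively and are based on observed data".
- 4.7 reproduces the protocol 16.8.2 text, replaces it with descriptive results only, and says that, given the limited sample size and the proof-of-concept phase, "hypothesis testing for secondary endpoints may not be considered appropriate and has been excluded from the SAP".

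For table layout, SAP 4.1.1 says: "Tables will be summarized by treatment group within each study part, as well as by pooled placebo across both study parts (if applicable").

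**The concern.** The objective asks how each dose differs from placebo, but the SAP plans only one-arm-at-a-time summaries. The reason given in 4.7 supports leaving out tests and p-values. It does not address estimation, yet the model-based difference and its interval are removed along with the tests.

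ISS and HSS are the two halves of the UAS. If UAS7 shows an effect, the natural next question is whether it comes from itch, hives or both. Under the SAP, the total gets a baseline- and stratum-adjusted MMRM contrast under missing at random, while the two parts get observed-case means. They would not be reported on the same basis. Anyone wanting a component difference would have to build one afterwards, although SAP 1 says the plan exists to avoid post hoc decisions.

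**Working it through.** **1. Does the protocol's model apply to ISS7 and HSS7?** Yes. SAP 3.4.1.2 gives them the same analysis-visit windows as UAS7, so each is derived at Weeks 1 to 6. They are continuous and repeated, which puts them under the repeated-measures branch of protocol 16.8.2 rather than the ANCOVA branch.

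**2. Does the SAP provide a difference or interval elsewhere?** No. The descriptive set in SAP 4.1.1 is N, n, mean, SD, SE, median, quartiles, minimum and maximum. CIs are mentioned there only as a rounding convention. The LS mean difference and its 90% CI are specified only in 4.4.3, for UAS7. The count is 3 doses × 2 scores = 6 contrasts, with 0 planned estimates.

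**3. Planning figures.** SAP 4.6 and protocol 16.4 give an 8-point UAS7 difference, SD 13, two-sided alpha 0.10, 34 per arm in Part 1, and 27 versus 43 for 25 mg against pooled placebo. Noncentral-t power is 80.7% for 34 v 34 and 79.9% for 27 v 43, so the stated 80% reproduces. Inflating for 10% withdrawal gives 34/0.9 → 38, 27/0.9 → 30 and 43/0.9 → 48, as planned.

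**4. Who is missing from a Week 6 observed-data summary?** Planned completers: 34 + 34 + 27 + 43 = 138. Randomized: 154. Difference: 16, or 10.4%. An MMRM would use whatever earlier weekly scores these subjects supplied.

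**5. How wide would the intervals be?** The documents give no SD for change in ISS7 or HSS7, so it is derived from the UAS7 SD. UAS7 is the sum of the two scores. With equal component SDs *s* and correlation *r* between the two changes (both assumptions):

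13 = *s* × √(2(1 + *r*)), so *s* = 13 / √(2(1 + *r*))

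- *r* = 0.3: *s* = 8.06
- *r* = 0.5: *s* = 7.51
- *r* = 0.9: *s* = 6.67

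Unadjusted 90% half-width = t(0.95; n1 + n2 − 2) × *s* × √(1/n1 + 1/n2).

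| Comparison | t | √(1/n1 + 1/n2) | *r* = 0.9 | *r* = 0.3 |
|---|---|---|---|---|
| 50 or 150 mg v pooled placebo (34 v 43) | 1.665 | 0.2295 | 2.55 | 3.08 |
| 25 mg v pooled placebo (27 v 43) | 1.668 | 0.2455 | 2.73 | 3.30 |
| Interim, Part 1 arms (34 v 34) | 1.668 | 0.2425 | 2.70 | 3.26 |

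If one SD is 1.5 times the other, the smaller is 13 / √(1 + 1.5² + 2 × 1.5*r*). The SDs then run from 5.33 (smaller, *r* = 0.9) to 9.57 (larger, *r* = 0.3), and the half-widths from 2.0 (34 v 43) to 3.9 (27 v 43).

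For scale only, SAP 3.4.1.2 says "The MID for ISS7 and HSS7 is considered a reduction in baseline of" at least 5 points. That is a within-subject change, not a between-group difference.

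No gain from baseline adjustment is included, because the documents give neither the baseline spread nor its correlation with change.

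**The case against.** **The change is declared.** SAP 4.7 quotes the protocol text, replaces it and gives a reason, and the SAP sections agree with each other. This stands: it is a documented choice, not a hidden contradiction. The point is that the reason covers only part of what was removed.

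**A comparative objective need not mean an adjusted contrast.** The safety objective is also worded against placebo and is summarized by arm. This is fair as far as the wording goes. The firmer basis is protocol 16.8.2, which assigned these endpoints a model.

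**A reader can form the difference.** The per-arm n, mean, SD and SE and the pooled placebo column allow a crude interval, and the half-widths above are of that kind. The figure would still be unplanned, unadjusted and limited to subjects observed at Week 6. How far it would differ from the MMRM result cannot be computed from the documents and may be small. Prior omalizumab users are capped at 20 of 154 and randomization is stratified. Subjects who stop drug are asked to stay to Week 6.

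**The sample is small.** If the 8-point UAS7 effect split equally, 4 points per component (an assumption), noncentral-t power over the equal-SD range above would be 64–78% for 27 v 43, 65–79% for 34 v 34 and 69–83% for 34 v 43. This supports not testing. It is not a reason to withhold an estimate.

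**The bases would still differ slightly.** A daily UAS needs both domains, while ISS7 and HSS7 each need only their own, and separate models need not sum to the UAS7 estimate. This is true, but the results would be much closer in kind than an MMRM contrast set beside observed-case means.

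**Six more unadjusted intervals invite over-reading.** If all six nulls were true and the contrasts independent, at least one 90% CI would exclude zero with probability 1 − 0.9⁶ = 47%, and less with positive correlation. Labelling reduces this risk but does not remove it.

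**Conclusion.** The concern holds. The SAP leaves 0 of 6 secondary efficacy contrasts with a pre-specified adjusted difference or CI, although the protocol planned them and the stated reason concerns testing only. At the planned withdrawal rate, about 16 of 154 subjects would contribute nothing to the Week 6 component summaries.

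The plan's own figures suggest usable intervals: half-widths of 2.6 to 3.3 points with equal component SDs and an assumed correlation of 0.3 to 0.9, or 2.0 to 3.9 if the SDs differ by a factor of 1.5. These rest on the planning SD of 13 and on assumed correlations and SD ratios.

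This should be changed, but it is not critical: the departure is disclosed and the primary UAS7 analysis is untouched.

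**What to change.** - **SAP 4.4.4:** fit the 4.4.3 MMRM to change in ISS7 and in HSS7, with treatment, week, treatment by week, omalizumab stratum and the score's own baseline. Report the Week 6 LS mean difference of each dose from pooled placebo with SE and 90% CI, without p-values. At the interim, use the Part 1 placebo group, in line with 4.4.6.3 for the primary endpoint: "Hypothesis testing will be based on the active arms in Part 1 versus the part 1 placebo group".
- **Labelling:** print with the results that they are descriptive estimation, not adjusted for multiplicity.
- **SAP 4.7:** limit the declared change for these two endpoints to dropping formal tests.
- **SAP 4.4.6.2:** amend the last sentence to except ISS7 and HSS7.

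The cost is wording in three places and re-use of the primary model code on two scores already derived with the same windows. No new data or subjects are needed. The remaining downside is that a 90% CI excluding zero may be read as an unadjusted 10% test, so the label must accompany every such table.

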#### ***4.4.5 Exploratory Endpoint Analysis Methods***

#### ***4.4.6 Statistical/Analytical Issues***

##### ***4.4.6.1 Adjustments for Covariates***

The MMRM to compare treatment groups for the primary endpoint will include a covariate adjustment for the baseline UAS7 value.

##### ***4.4.6.2 Handling of Dropouts or Missing Data***

For assessment of responder endpoints, subjects with missing data at the time point of interest will not be analyzed; only observed values will be used.

Derivations of the weekly UAS7, ISS7, [REDACTED] scores will consider the minimum daily score requirement and management of missing scores as defined in [Section 3.4.1.1](#).

The [REDACTED] data collection does not allow for individual questions to be skipped within a questionnaire response; therefore, the management of missing scores relative to the derivation of each total score and the dimension scores is not required.

For the primary endpoint, treatment groups will be compared for observed and change from baseline in weekly UAS7 score using a MMRM. The model will include fixed treatment group by week interaction, the stratification factor of prior omalizumab use (randomization strata), and the UAS7 baseline value as a covariate. The Kenward and Roger method will be used to calculate the denominator degrees of freedom for the test of fixed effects. All other endpoints are summarized descriptively and are based on observed data.

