16.2. Estimand

Consistent with the International Council for Harmonisation (ICH) Guideline E9 (R1) addendum on estimands and sensitivity analysis in clinical trials to the guideline on statistical principles for clinical trials ([FDA 2021](#)), the definition of the attributes of the primary estimand of this study is provided in this section.

The primary estimand of the study is to assess the difference in disease activity in pruritus and hives in subjects with CSU treated with EP262 or placebo, as measured by change in weekly UAS7 after 6 weeks of randomized treatment, regardless of treatment discontinuation and use of prohibited and/or rescue medications.

The population targeted by the scientific question is defined via the inclusion and exclusion criteria as part of the protocol. A key aspect of eligibility is that subjects must have moderate-to-severe disease activity in CSU at baseline, defined as a UAS7 of at least 16.

Premature discontinuation from study drug and use of prohibited and/or rescue medications are the primary potential intercurrent events that could occur. The treatment policy strategy is used for the primary estimand, consistent with the intent-to-treat principle.

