## 4.2 Analysis Sets

The analysis sets are defined as follows:

- Full Analysis Set: All subjects who are randomized and take at least 1 dose of randomized study drug will be included in the Full Analysis Set (FAS). Subjects in the FAS will be analyzed according to randomized treatment assignment. All efficacy and PD analyses will be based on the FAS.
- Safety Analysis Set: All subjects who are randomized and take at least 1 dose of randomized study drug will be included in the Safety Analysis Set. Safety analyses will be based upon treatment actually received.
- PK Set: All subjects who receive at least 1 dose of EP262 and provide adequate blood samples for bioanalysis will be included in the PK Set.

Data summaries to be presented on both the Safety Analysis Set and the Full Analysis Set will only be produced on both analysis sets if there is a difference in the population groups.

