### **4.4 Efficacy Evaluation**

#### **4.4.1 Datasets Analyzed**

All efficacy summaries will be based on the Full Analysis Set. A data listing of subjects excluded from the Full Analysis Set, to include the reason for exclusion, will be presented.

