#### **4.4.3 Primary Efficacy Endpoint Analysis Methods**

The core attributes of the estimand for the analysis of the primary endpoint are as follows:

- **Population:** The primary endpoint will be analyzed among all subjects in the Full Analysis Set. The population is further defined via the inclusion and exclusion criteria as part of the protocol. A key aspect of eligibility is that subjects must have moderate-to-severe disease activity in CSU at baseline, defined as a UAS7 of at least 16.
- **Treatment Conditions:** Participants are randomized in a 1:1:1 ratio to receive 50 mg of EP262, 150 mg of EP262, or placebo in Part 1 and randomized in a 3:1 ratio to receive 25 mg of EP262 or placebo in Part 2, to receive once daily drug administration during a 6-week Double-Blind Treatment Period. The primary analysis will compare each active EP262 group to Placebo at Week 6.
- **Endpoint:** The primary efficacy endpoint is the change from baseline in UAS7 at Visit 4 (Week 6).
- **Summary Measure:** The difference in model-adjusted means between each EP262 treatment group and Placebo in the change from baseline weekly UAS7 value.
- **Handling of Intercurrent Events (ICEs):** Potential ICEs that a subject may experience on study include:
  - Premature discontinuation from study drug as described in Section 8.6.1 of the clinical study protocol.
  - Use of prohibited and/or rescue medication as described in Section 8.2 (Subject Exclusion Criteria) of the clinical study protocol and [Section 3.3.1.2](#) of the SAP, respectively.

Subjects who experience an ICE prior to Week 6 will have data collection handled by the treatment policy strategy, consistent with the intent-to-treat principle.

Placebo subjects in Part 1 and Part 2 (if available) will be pooled for the treatment comparison analysis. The null hypothesis to be tested is that there is no difference in the mean change from baseline between EP262 (each dose level) and Placebo:

$$H_0: \mu_A = \mu_P;$$

Where  $\mu_A$  and  $\mu_P$  represent the mean change from baseline values for EP262 and Placebo, respectively. The alternate hypothesis to be tested is that the treatment group means differ:

$$H_1: \mu_A \neq \mu_P;$$

[figure not shown]

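### Responder rates are reported on observed cases only, with no full-FAS rate or sensitivity analysis to show the effect of missing data

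*SAP*

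**What the plan says.** SAP 4.4.6.2 opens with the responder rule: "subjects with missing data at the time point of interest will not be analyzed; only observed values will be used". It closes by saying of everything except the primary endpoint: "All other endpoints are summarized descriptively and are based on observed data". Both statements follow the default in SAP 4.1.1, where, unless noted otherwise, "the denominator to determine the percentage of subjects in each category will be based on the number of subjects with available data". SAP 4.4.1 adds: "All efficacy summaries will be based on the Full Analysis Set". SAP 4.2 defines that set by randomization and at least one dose.

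A value can be missing for two reasons. The subject may have left the study. Or, for an endpoint built on a weekly diary score, a subject still in the study may have completed fewer than 4 daily scores in a full week (SAP 3.4.1.1, with a proportionate rule for shortened weeks). Subjects who stop study drug are asked to stay and be assessed (Protocol 8.6.1); if they have a value, the rule keeps them.

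The primary endpoint is handled differently. Its MMRM uses all post-baseline weeks of the treatment period and assumes missing at random (SAP 4.4.3). SAP 4.7 drops the protocol's multiple imputation for the primary endpoint, the Per Protocol Set, and all testing of secondary and exploratory endpoints, including the stratified test for response proportions. The visible text names no responder endpoint; the exploratory sections are blacked out.

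**The concern.** An observed-case proportion is unbiased for an arm only if, within that arm, missingness is unrelated to response. The MMRM needs this only after conditioning on the scores already seen. A subject who worsens and leaves after Week 4 still informs the Week 6 UAS7 estimate through Weeks 1 to 4, but disappears from the Week 6 responder rate. The SAP gives no reason for treating the same subject in these two ways.

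The arms are small, so a few missing subjects are visible in a percentage. The rates carry no p-values, but they will still be read. The full result package is delivered at the Part 1 interim and again at the end (SAP 4.4.6.3), and Protocol 5.2 says the results will guide further development and the design of confirmatory studies. A flattering or diluted responder rate could feed into dose choice or a later sample size.

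**Working it through.** **The plan's own figures.** The documents give no figure for responder endpoints. Protocol 16.4 gives about 10% early withdrawal and 30, 38, 38 and 48 randomized to 25 mg, 50 mg, 150 mg and placebo. The enrolment figures agree with that: 34/0.90 = 37.8, so 38; 27/0.90 = 30; 43/0.90 = 47.8, so 48. The stated 80% power for the primary endpoint also reproduces (80.7% for 34 per arm and 79.9% for 27 versus 43; noncentral t, difference 8, SD 13, two-sided alpha 0.10), but it has no bearing on responders.

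**Subjects left out.** Ten percent of 30, 38, 38 and 48 is 3, 3.8, 3.8 and 4.8, so about 3, 4, 4 and 5 subjects. In an arm of 38, one subject is 1/38 = 2.6 points. Missed diary weeks among subjects still in the study would add to these counts.

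**Formula.** Let p be the rate in observed subjects, q the rate the missing subjects would have had, and d the share missing. The full-FAS rate is (1 − d)p + dq, so the observed-case rate is off by p − [(1 − d)p + dq] = d(p − q). Only d = 10% comes from the documents; p, q and any split of d by arm are assumptions.

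**One arm, d = 10%, missing counted as non-response (q = 0).**

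| Observed rate p | Full-FAS rate 0.90p | Excess |
|---|---|---|
| 20% | 18% | 2 points |
| 30% | 27% | 3 points |
| 40% | 36% | 4 points |
| 50% | 45% | 5 points |

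**The sign depends on q.** At p = 40% and d = 10%, the error 0.10 × (40 − q) is +4 points at q = 0%, +2 at q = 20%, 0 at q = 40%, −2 at q = 60% and −6 at q = 100%.

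**Between arms, assumed observed rates 40% versus 20%, q = 0.** The observed-case difference is 20 points. The full-FAS difference is 40(1 − d1) − 20(1 − d2), with d1 missing on drug and d2 on placebo.

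| d1 / d2 | Full-FAS rates | Difference |
|---|---|---|
| 10% / 10% | 36% vs 18% | 18 points |
| 15% / 5% | 34% vs 19% | 15 points |
| 5% / 15% | 38% vs 17% | 21 points |
| 20% / 0% | 32% vs 20% | 12 points |
| 0% / 20% | 40% vs 16% | 24 points |

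So the observed-case rule overstates the difference in some scenarios and understates it in others. An observed tie shows the same: 25% versus 25% becomes 25 × 0.95 = 23.8% versus 25 × 0.80 = 20% with 5% missing on drug and 20% on placebo, and the reverse with the split reversed.

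**The case against.** The strongest reply is that the SAP is open and consistent about this. Available-data denominators are its declared default. The same section makes all non-primary endpoints descriptive and observed-case. SAP 4.1.1 already tabulates N, n and the count in each category, so a reader can divide responders by N. Disposition and reasons for discontinuation are also summarized by arm (SAP 4.3.1). The primary and secondary endpoints are continuous, no responder endpoint is tested, and counting missing as failure is itself an untested assumption. All of this stands and keeps the point small. It does not supply the missing percentage or a reason for making the observed-case rate the only one printed.

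A reader might also infer that the rule breaks the treatment-policy approach. The documents do not support that. Protocol 16.2 says: "The treatment policy strategy is used for the primary estimand, consistent with the intent-to-treat principle". SAP 4.4.3 limits the scope in the same way: "The core attributes of the estimand for the analysis of the primary endpoint are as follows". The strategy takes outcomes "regardless of treatment discontinuation and use of prohibited and/or rescue medications"; it deals with those events, not with values that were never collected. Subjects who stop drug or take rescue medication but have data stay in the responder rate.

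Nor does the rule contradict the FAS. That set is defined by randomization and dosing and says nothing about missing outcomes, so an observed-case summary within it is at most a tension in wording.

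**Conclusion.** The point holds in a limited form. Responder rates are observed-case, the earlier data on missing subjects go unused, and nothing in the visible plan shows how much this matters. At 10% missing, with no missing subject a responder, rates of 20% to 50% are overstated by 2 to 5 points. With missingness that differs by arm, the difference between arms can move in either direction.

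Two stronger conclusions are not established. Upward bias requires missing subjects to respond less often than observed ones; that is plausible for those who leave for lack of effect, but the documents give no figure, and the error is zero or negative once q reaches or exceeds p. A reversal of the treatment comparison is not shown either: across the scenarios from a 20-point difference, the sign never changes, and the tied example starts from no difference.

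The consequence is modest because the affected results are descriptive and appear to be exploratory. Which endpoints are involved cannot be seen.

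**What to change.** Replace the responder sentence in SAP 4.4.6.2 with wording such as: *For responder endpoints, the denominator is all FAS subjects in the arm, and a subject with no value at the time point is counted as a non-responder. The observed-case rate, the number with data and the FAS N are shown beside it by arm.* SAP 4.1.1 allows exceptions to its default denominator, so it needs no change. Multiple imputation is a reasonable alternative for the full-FAS rate, but it needs a specified model.

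The cost is one SAP sentence and one extra table column; n and N are already planned, and the observed-case result is kept. The downside is that a subject who misses a diary week for administrative reasons counts as a non-responder, which slightly lowers rates. Printing both rates lets the reader see how much of the gap comes from that.
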